Given the anticipated differences in patients who seek care in these settings, we propose using propensity score techniques to balance patient characteristics in the two treatment groups both within and across sites. We will use relatively new methods developed for use of propensity scores in the context of multilevel data.⁴² We look towards using propensity scores for achieving balance in the distributions of covariates to allow for a causal comparison. Our treatment assignment is at the individual level and we propose using appropriate propensity weighting methods to generate valid causal inferences, under the assumption of absence of unmeasured confounders.

For causal comparisons, we adopt the potential outcome framework for causal inference.⁴³ Under the standard stable unit treatment value assumption (SUTVA)⁴⁴, which states that the outcomes for each patient are unaffected by the treatment assignments of the other patients, each patient has two potential outcomes corresponding to the two treatments (ED or IC care), only one of which is observed for each patient. We believe the SUTVA assumption to be true in our setting. We aim to estimate the population average treatment effect, although we may also look at the *population average treatment effect on the treated (ATT)*, which we expect will be very similar.

Notation Let $k = 1, 2, \dots, K$ denote number of regions and $i=1, 2, \dots, n_k$ denote the number of participants in region k . Total sample size is $n = \sum_{k=1}^K n_k$. Each subject belongs to one of two groups, ED (control) or IC (treatment) care. Let Z_{ki} be the binary variable indicating whether the subject is in the treatment ($Z=1$) or control ($Z=0$) group. Also, let U_{ki} be a vector of subject-level covariates and V_k be a vector of region-level covariates, and $X_{ki} = (U_{ki}, V_k)$. For each subject, an outcome Y_{ki} is observed, which, in our study, can be continuous or binary. The propensity score is defined as $e(X_{ki}) = \Pr(Z_{ki}=1 | X_{ki})$.

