Fitting a Propensity Model Given the multi-region (clustered) data, we cannot use standard techniques for propensity score modeling but instead will use a *random effects model* that accounts for clustering. We have chosen this model because we are uncertain about all of the cluster-level covariates that might impact on treatment effect. The few that we hypothesize to be regional-level confounders, as described above, we will include in the model. The individual level covariates will include: SCD complications, self-reported number of acute care visits and hospitalizations in the prior 12 months, pain rating upon first arrival for care, distance from residence to site of care, and demographic variables. The random effects model to generate the propensity score is as follows:

$$\text{logit}(e_{ki}) = \delta_k + X_{ki} \beta \quad (1)$$

This model includes individual level covariates, as well as cluster-specific intercepts due to measured and unmeasured cluster-level covariates, and a prior distribution for cluster-level main effects, $\delta_k \sim N(0, \sigma_\delta^2)$. We expect that since we will have many patients within each region (cluster), we should not have any difficulty in fitting the random-effects model. The goodness of fit of this model will be checked by conventional diagnostics of covariate balance between the ED and IC treated patients, checking the overall and within-region balance of the weighted distribution of covariates in the two groups.

Estimating an Overall Treatment Effect We will then use the inverse of the propensity score, e_{ki} , generated from the random effects model described above, to *weight the outcomes* for each individual. This will allow us to draw valid inferences about the differences between groups. We propose using a non-parametric clustered-estimator as our inverse-probability-weighted estimator.

$$\hat{\pi} = \frac{\sum_{k=1}^K \hat{\pi}_k w_k}{\sum_k w_k} \quad (2)$$

Where $w_k = \sum_{i \in k} w_{ki}$, $w_{ki} = Z_{ki}/e_{ki} + (1-Z_{ki})/(1-e_{ki})$, and $\hat{\pi}_k$ is the inverse-propensity weighted treatment effect for the k -th region. This estimator accounts for clustering of the patients by region. The standard error of the estimate will be generated by bootstrapping.

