We have based the needed sample size on the outcome requiring the most participants, the admission rate from the ED v. IC. We hypothesize that we will observe an ED admission rate of 50%⁹, and an IC admission rate of 27% (an absolute reduction of at least 23%). We took the following design considerations into account in estimating the sample sizes needed to detect this difference: We have a 2-arm study (IC vs. ED) with 4 clusters (sites) per arm. With a type I error of 0.05, a type II error of 0.20 (power 0.80), and an estimated intracluster correlation coefficient (ICC) of 0.02, we will require an average of 41 participants in each cluster (site) per arm. 410 participants total (205 per arm) are required to detect our hypothesized difference in admission rate. We estimate we will observe a lost-to-follow-up rate of 18% so our total required sample size is [410/(1-0.18)] = 500 participants.

b. Early stopping rules. NA

8. Risks

a. Medical risks, listing all procedures, their major and minor risks and expected frequency.

The risks from this study are minimal. The participants may become tired or bored while filling out the surveys. There is also the risk of loss of privacy. Participants can choose to not participate in this study as it is not a treatment protocol there are no alternatives.

b. Steps taken to minimize the risks. All primary data to be collected will be de-identified using a unique identifier and will be kept in a secure office in a password protected computer. The data put in REDCap will be de-identified. As REDCap is a secure website and only deidentified data will be put in it the risk of loss of privacy is minimal. Every attempt will be made to assure that all locally collected data is kept in a secure environment and that all identifiers will be removed from primary data. The spreadsheet with the identifying info linked to the unique identifier will be destroyed when the REDCap database is finalized and locked.

c. Plan for reporting unanticipated problems or study deviations. Any breach of patient confidentiality will be reported to the IRB.

- d. Legal risks such as the risks that would be associated with breach of confidentiality.NA
- e. Financial risks to the participants. NA

9. Benefits

- a. Description of the probable benefits for the participant and for society.

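### The Section 7a sample-size figures contradict each other (41 per cluster gives 328, not 410), and the stated 80% power is not the power of the planned weighted estimator

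*Combined protocol and SAP*

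**What the plan says.** Section 7a bases the sample size on admission, the outcome said to need the most participants. The inputs are an ED rate of 50%, an IC rate of 27%, type I error 0.05, power 0.80 and an ICC of 0.02. The design is given as "We have a 2-arm study (IC vs. ED) with 4 clusters (sites) per arm". The result is that "we will require an average of 41 participants in each cluster (site) per arm", followed by a total of 410 (205 per arm), raised to 500 for 18% loss to follow-up.

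The rest of Section 7 describes a different structure. There are four regions in all. On exposure it says "Our treatment assignment is at the individual level". Eq 2 forms an inverse-propensity-weighted IC-versus-ED effect inside each region and averages the four, with a bootstrap standard error; the plan adds that "This estimator accounts for clustering of the patients by region". The same estimator is to be used for admission. Section 7 also names regional influences on outcome, among them how long the infusion center has been open and how crowded the ED is.

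**The concern.** There are two problems.

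First, the number per cluster, the number of clusters and the total cannot all be right. The enrolment target of 500 is built on the total.

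Second, the calculation describes two sets of four clusters compared between arms, whereas Eq 2 compares settings within regions using weights. Two features of Eq 2 are not dealt with:

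- **Weights.** Unequal weights reduce the effective sample size. Section 7 expects patients in the two settings to differ, which is the situation in which weights become variable.
- **What the ICC refers to.** A region component shared by the ED and the IC cancels in a within-region contrast. A component specific to a facility, or an IC–ED effect that varies by region, does not.

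At stake is whether a reader can tell what admission difference the study can detect.

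**Working it through.** **Inputs from Section 7a.** p₁ = 0.50, p₂ = 0.27, d = 0.23, ICC = 0.02, k = 4 clusters per arm. Sidedness is not stated; two-sided 0.05 is assumed.

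**1. Internal arithmetic**

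- 41 × 4 = 164 per arm; × 2 = 328, not 410.
- 205/41 = 5 clusters per arm, but there are four sites. 205/4 = 51.25 per cluster.
- 410/(1 − 0.18) = 500 is correct.

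**2. Trying to reproduce 410**

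Variance term V: unpooled 0.25 + 0.1971 = 0.4471; pooled 2 × 0.385 × 0.615 = 0.4736. With design effect 1 + (m − 1) × 0.02, the size needed for 80% power is:

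| Method, 4 clusters per arm | m per cluster | Total |
|---|---|---|
| Normal approximation | 25–27 | 200–216 |
| Formula adding one cluster per arm | 39 | 312 |
| Non-central t, 6 df, unpooled | 46 | 368 |
| Non-central t, 6 df, pooled | 51 | 408 |

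Of the formulas tried, only the last comes close to 410. The 312 from the second row is nearer to 328. So the text does not show which of 41 and 410 is the slip.

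**3. Power of the cluster model**

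SE = √(V × [1 + (m − 1) × 0.02] / (k m)); power from the non-central t with 2(k − 1) df.

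- m = 51.25, k = 4 (410): design effect 2.005, SE 0.066–0.068, power 80–82%.
- m = 41, k = 4 (328): design effect 1.8, SE 0.070–0.072, power 76–78%.
- m = 41, k = 5 (410): 8 df, power 88–89%.

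**4. Power of Eq 2 at 410, region component cancelling fully**

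SE = √(V × f / 205), where f is the weighting design effect. The documents give no f, so the values are assumptions. Power = Φ(0.23/SE − 1.96).

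- f = 1: SE 0.047–0.048, 99.8%.
- f = 1.5: SE 0.057–0.059, 97–98%.
- f = 2: SE 0.066–0.068, 92–94%.
- f = 3: SE 0.081–0.083, 79–81%.

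Without weighting or clustering, about 66–70 per arm would be needed. Power therefore reaches 80% at f = 205/70.3 = 2.9 (pooled) to 205/66.3 = 3.1 (unpooled).

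**5. Power of Eq 2 at 410, facility-level ICC of 0.02 remaining**

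The weighting loss is applied to the cluster size, m* = 51.25/f, and SE = √(V × [1 + (m* − 1) × 0.02] / (4 m*)).

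| f | SE | Normal | 6-df t |
|---|---|---|---|
| 1 | 0.066–0.068 | 92–94% | 80–82% |
| 1.5 | 0.074–0.076 | 86–88% | 71–74% |
| 2 | 0.081–0.083 | 79–81% | 64–66% |

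A facility-level ICC of 0.02 implies an SD of the IC–ED contrast across regions of about √(2 × 0.02 × 0.385 × 0.615) = 0.10. A simulation of Eq 2 (410 patients, four regions, weight inflation about 1.3, normal reference) gave about 97%, 90% and 73% power at assumed between-region SDs of the effect of 0.05, 0.10 and 0.15.

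**6. The unit counted**

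Section 4a captures acute visits over 18 months. Section 3 reports 2.5 visits per person per year at the Baltimore center, or 2.5 × 1.5 = 3.75 over follow-up. One participant may use both settings, so 205 per arm has no defined meaning.

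**The case against.** The strongest reply is that eight facility clusters, four per arm, is a reasonable planning model. The ED and the IC in a region are separate facilities, and two of the regional influences named in Section 7 act on one setting only. Section 3 shows infusion centers differing in discharge home: 85% in Baltimore, 96.5% in Milwaukee. Individual-level exposure does not remove facility variance. This stands. A reader might infer that the ICC simply cancels in Eq 2 and should be dropped; the documents do not support that, and at weighting factors of 1.5–2.0 dropping it would report 92–98% where 64–88% may apply.

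A second reply is that the cluster model is conservative, so no harm follows. That may be so, but it depends on the weighting loss and the between-region variation, neither of which is given, and it does not reconcile 328 with 410.

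A third is that admission is a secondary outcome. For the primary outcome, Section 3 gives 190 minutes in the Baltimore ED (from triage, SD 129.8) against 57.7 in its infusion center (from arrival). Using that SD in both groups, 2 × 129.8² × 7.85 / 132.3² is about 15 per arm before design or weighting effects. This limits the consequence, but admission is the outcome on which the plan chose to justify its size.

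Finally, the 6-df t is a reconstruction: Section 7a names no formula, variance form or degrees of freedom. That is accepted, and is part of the point.

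**Conclusion.** Wrong as written. The contradiction between 41 per cluster and 410 in total is plain arithmetic and rests on no assumption. It also holds that the stated 80% power does not describe Eq 2, because the weights are left out and the meaning of the ICC is left open.

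The size of the second part depends on inputs the plan does not give. At 410 and assumed weighting factors of 1.5–2.0, power is about 92–98% if the region component cancels fully. With a facility-level ICC of 0.02 it is about 79–88% (normal) or 64–74% (6-df t). These figures assume equal arms, one outcome per participant and a two-sided test.

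A reader might infer that the study is underpowered. The documents do not show that: if the region component cancels, 410 keeps 80% power until the weighting factor reaches about 2.9. What they show is that the power is not known from the plan.

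**What to change.** Rewrite the Section 7a paragraph:

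- Reconcile 41 per cluster with 410, and name the formula, including the variance form and the reference distribution.
- State power, or the detectable difference, for Eq 2 at 410 analysable participants, with a stated weighting design effect (for example 1.5–2.0, labelled as an assumption and later checked against the observed weights).
- Say whether the ICC of 0.02 is shared by both settings or specific to the facility, and state an assumption for between-region variation of the IC–ED effect. Do not simply remove the ICC; show the range.
- Define how a participant with repeat visits, or with visits to both settings, counts toward 205 per arm.

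The cost is one paragraph and a short calculation or simulation. Enrolment does not change. The downside is that the stated power may become less favourable.

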
A similar clinic to the SCIC opened at Froedtert Hospital in Milwaukee (FASCC) in 2011. The FASCC clinic is open weekdays and serves the needs of 300 adults with SCD. The average length of stay in the clinic is 3 hours and 96.5% of visits end with the patient being discharged home. Since this clinic opened there has been a 38% decrease in admissions and a decrease in 30 day readmissions from 61 to 28%.

Without a direct comparison of ED to IC, many argue that there is something different about the patients that receive care in an ED versus those that seek care in an IC. Further, the recent expansion in ICs has been driven primarily by economic consideration (length of stay, readmissions), rather than by patient-centered outcomes, on which there is a lack of data. Demonstrating attainment of important clinical outcomes in ICs may increase their stability and viability. **With this proposal we will demonstrate that the improved outcomes seen in an IC v. the ED are not due to differences in the type of patients seen for care but rather in the processes of care for VOC in these two sites.**

4. Study Procedures

- a. Study design, including the sequence and timing of study procedures (distinguish research procedures from those that are part of routine care).

We will prospectively enroll patients that are seen in participating centers into a study cohort. We will then capture data from their acute visits. We will enroll participants from 4 sites: Baltimore, Cleveland, Milwaukee and Baton Rouge. When any participant is treated in either an ED or IC, data on clinical outcomes and patient experiences of care will be collected.

Baseline data collection will include: SCD genotypes and co-morbidities³⁵

- a. AVN
- b. Gall bladder disease
- c. Sickle chronic lung disease
- d. Leg ulcer
- e. Priapism (male)
- f. Renal failure
- g. Retinopathy
- h. Stroke

2. Self-reported number of acute care visits and hospitalizations in the prior 12 months
3. Daily chronic pain using the Numeric Rating scale (NRS).
4. Prior and current treatments, including:
 - a. hydroxyurea use
 - b. chronic transfusions
 - c. pain medications, (specific regimens used to treat chronic daily or intermittent pain)

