All data collection will be done using RedCap. RedCap is a secure web based database tool that has multisite functionality. Each external site will enter their data into a single database. Each external site will only have access to their own data through the site. As the central coordinating site, Hopkins will have access to all of the data. When data collection is complete and records are finalized the data will undergo data lock. As all data will be entered into a common database merging of data will be done after data is exported from RedCap into Stata for further analysis. Merging of data will need to be done for combining the demographic data with data collected from each acute visit.

5. Inclusion/Exclusion Criteria

All individuals with confirmed SCD who live within 60 miles of the study center or who already receive regular care at the participating centers will be eligible for enrollment. The only exclusions will be patients who are pregnant, who have been stable on chronic transfusion therapy and have not had a painful episode within two years of enrollment (transfusions may prevent all acute painful events) and patients who are unwilling or unable to sign consent.

6. Drugs/ Substances/ Devices

- a. The rationale for choosing the drug and dose or for choosing the device to be used. NA
- b. Justification and safety information if FDA approved drugs will be administered for non-FDA approved indications or if doses or routes of administration or participant populations are changed. NA
- c. Justification and safety information if non-FDA approved drugs without an IND will be administered. NA

Date: _____
 Principal Investigator: _____
 Application Number: _____

7. Study Statistics

Primary and secondary outcome variables: This is an observational study from which we will draw inferences about outcomes of care attributable to the treatment setting. As we are not randomizing patients to ED care or to IC care, we must control for confounders in the relationship between site of care and outcomes. We note, however, that there may be regional differences that impact on outcomes: percentage of high utilizers in the region, duration IC has been functioning, and ED crowding. In our study, we have clustering of individual patients by regions (n=4). We will account for both known and unknown confounders at the level of the regions.

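### The sample-size figures do not multiply: four sites at 41 per site per arm give 328 evaluable participants (400 enrolled), but the plan states 410 (500 enrolled)

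*Combined protocol and SAP*

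**What the plan says.** All the figures are in section 7 (Study Statistics), item a. The study is sized on the admission rate, 50% in the ED against 27% in the IC, with type I error 0.05, power 0.80 and ICC 0.02. The layout is given as "We have a 2-arm study (IC vs. ED) with 4 clusters (sites) per arm". From these inputs the plan says "we will require an average of 41 participants in each cluster (site) per arm", then "410 participants total (205 per arm) are required to detect our hypothesized difference in admission rate". After an 18% allowance for loss to follow-up, it concludes that "our total required sample size is [410/(1-0.18)] = 500 participants".

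The number of sites agrees elsewhere. Section 4, item a says "We will enroll participants from 4 sites: Baltimore, Cleveland, Milwaukee and Baton Rouge", and the opening of section 7 also counts four regions.

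**The concern.** Sites per arm, participants per site per arm, and participants per arm are linked by one multiplication, and here it fails. The word 'average' does not help, because an average of 41 over four sites still totals 164.

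This paragraph is the only justification for enrolling 500. As printed, a reader cannot tell whether the stated 80% power belongs to 328 or to 410 evaluable participants. Three practical matters depend on the answer:

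- **Recruitment target per site.** Four sites that each reached 41 per arm would stop 82 short of the stated requirement.
- **Tolerable attrition.** With 500 enrolled, the study can lose 18% if 410 are needed (1 − 410/500), but 34.4% if 328 are needed (1 − 328/500).
- **Reproducibility.** No formula or sidedness is given, so the calculation cannot be checked.

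**Working it through.** **Inputs, all from section 7, item a:** 2 arms; 4 sites per arm; 41 per site per arm; 410 in total and 205 per arm; 18% loss; 500 enrolled; rates 0.50 and 0.27; α = 0.05; power 0.80; ICC = 0.02. Sidedness is not stated, so two-sided is assumed.

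**Step 1: the plan's own loss adjustment.** 410/(1 − 0.18) = 410/0.82 = 500. Also 205 × 2 = 410. These figures agree with each other.

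**Step 2: from sites to total.** 4 × 41 = 164 per arm; 164 × 2 = 328; 328/0.82 = 400. Against the stated total, 410 − 328 = 82 and 410/328 = 1.25.

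**Step 3: the per-site average that 410 implies.** 410/(4 × 2) = 51.25.

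**Step 4: do the design inputs favour one figure?** Let m be the number per site per arm, with k = 4 clusters per arm.

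- Design effect: DE = 1 + (m − 1) × 0.02, which is 1.80 at m = 41 and 2.005 at m = 51.25.
- Variance term V: unpooled 0.50 × 0.50 + 0.27 × 0.73 = 0.4471; pooled 2 × 0.385 × 0.615 = 0.47355.
- Standardised difference: λ = 0.23/√(V × DE/(4m)). At m = 41 it is 3.283 (unpooled) or 3.190 (pooled). At m = 51.25 it is 3.478 or 3.380.
- Power: normal, Φ(λ − 1.960); t/normal, Φ(λ − 2.447); t/t, the t distribution function on 6 df at λ − 2.447; or the noncentral t on 6 df. Here 6 = 2(k − 1).

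| Formula | Variance | m for power 0.80 | Power at 41 (328) | Power at 51.25 (410) |
|---|---|---|---|---|
| Normal | unpooled | 24.3 | 0.907 | 0.936 |
| Normal | pooled | 26.5 | 0.891 | 0.922 |
| t/normal | unpooled | 41.2 | 0.799 | 0.849 |
| t/normal | pooled | 46.0 | 0.771 | 0.825 |
| t/t | unpooled | 44.3 | 0.783 | 0.829 |
| t/t | pooled | 49.6 | 0.757 | 0.807 |
| Noncentral t | unpooled | 45.1 | 0.781 | 0.824 |
| Noncentral t | pooled | 50.5 | 0.758 | 0.803 |

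One of the eight variants gives about 41. A different one comes closest to 51.25 (50.5 per site per arm, 404 in total). None gives both. One match among eight is weak evidence of how 41 arose, so the table does not settle which figure is wrong.

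**Step 5: would a fifth site explain it?** As multiplication, yes: 41 × 5 × 2 = 410. As a power calculation, no. With k = 5 and 8 df for the t-based forms, the same eight variants need only about 18 to 28 per cluster per arm for 80% power, not 41.

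**The case against.** The strongest reply is that nothing operational depends on the slip. The figures that govern enrolment (205, 410 and 500) agree with each other, and only the intermediate 41 does not fit. At 410 the stated 80% power is met under all eight variants in the table. Correcting the paragraph changes no endpoint, analysis or enrolment target, and the outcome used for sizing is a secondary one. All of this stands, and it is why the point is a should-fix. It does not remove the contradiction: nothing printed links 41 per site to 205 per arm.

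A reader might go further and infer one of three things:

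- **The study is underpowered.** The documents do not support this. The stated total is the larger of the two, and it reaches 80% power under the plan's own inputs.
- **A fifth site was planned.** The multiplication is suggestive, but no fifth site is described, and step 5 shows that a five-cluster calculation would not produce 41.
- **The 41 is simply a misprint.** This is possible, since the later figures agree among themselves. However, 41 also has a plausible derivation at four sites (41.2), so the text cannot decide between a wrong 41 and a wrong 410.

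**Conclusion.** The inconsistency is certain from the printed text: 164 against 205 per arm, 328 against 410 evaluable, 400 against 500 enrolled, and 41 against 51.25 per site per arm. Which figure is wrong cannot be determined from the documents.

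The consequence is limited. Power at 410 is about 0.80 to 0.94. At 328 it is about 0.76 to 0.91, and below 0.80 under all six t-based variants (0.757 to 0.799). These ranges assume a two-sided test, equal arms and four clusters per arm, with the plan's rates and ICC. Severity: should-fix.

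**What to change.** Reconcile the paragraph in one of these ways. The authors must choose, because only they know the calculation behind it.

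1. Correct the per-site average to 51.25 (about 51 to 52 per site per arm) and keep 410 and 500. Print the unrounded average, or say that it is rounded, because 51 × 8 = 408.
2. Keep 41 and state the allowance that takes 328 to 410.
3. Restate the requirement as 328 evaluable and 400 enrolled, and describe 500 as a margin above it. Before doing so, confirm that 328 gives 80% power under the formula actually used, since no t-based variant tried here reaches it.

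In each case state the formula (variance form, normal or t, degrees of freedom), the sidedness, and the power at the total kept. The cost is one rewritten paragraph, and the enrolment target of 500 can stand under any of the three.

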After participants have consented they will be asked to contact by phone or email the research assistants about all acute care visits. In addition, the research assistant will review the daily census for IC's and ED's at the local site to identify participants with an acute care visit. Furthermore, each participant will be contacted by phone monthly and asked about acute care visits.

Once an acute care visit for an uncomplicated VOC has occurred, the following data will be collected: Time crisis started, Arrival time, Triage time, Pain level on arrival, Time to first dose of opioid, Time from first dose to nurse reassessment of pain, Time in the ED/IC, Pain level at discharge from ED/IC, Change in pain scale from arrival to discharge, Disposition at time of discharge from ED/IC (home, admit, etc.). In order to assess patient experiences of care in the acute setting, participants will be surveyed either toward the end of their acute visit or by phone within 72 hours of their visit. As reinforcement, at each monthly call, we will verify contact information and encourage participants to call us within 3 days of any acute visit. The survey tools that will be used include the Painful Crises Experiences of Care for SCD tool (PEPS); a survey of safety and a survey of patient satisfaction with ED pain management.

- b. Study duration and number of study visits required of research participants. Participants will be part of the study for 18 months. During which time there will be no in person study visits. There will be monthly phone calls and contact at the time of acute care visits.
- c. Blinding, including justification for blinding or not blinding the trial, if applicable. NA
- d. Justification of why participants will not receive routine care or will have current therapy stopped. NA
- e. Justification for inclusion of a placebo or non-treatment group. NA
- f. Definition of treatment failure or participant removal criteria. NA
- g. Description of what happens to participants receiving therapy when study ends or if a participant's participation in the study ends prematurely. NA

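### The inflation from 410 to 500 allows only for loss to follow-up, so 410 analysable participants are reached only if every retained participant has an uncomplicated VOC visit

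*Combined protocol and SAP*

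**What the plan says.** Section 7a sizes the study on admission rate, 50% in the ED against 27% in the infusion center (IC). The design is "We have a 2-arm study (IC vs. ED) with 4 clusters (sites) per arm", and the parameters are "With a type I error of 0.05, a type II error of 0.20 (power 0.80), and an estimated intracluster correlation coefficient (ICC) of 0.02". It states that "we will require an average of 41 participants in each cluster (site) per arm" and gives a total of 410 (205 per arm). The last step is "We estimate we will observe a lost-to-follow-up rate of 18% so our total required sample size is [410/(1-0.18)] = 500 participants".

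Section 4a enrols a cohort first and follows it for 18 months, with monthly calls and no study visits in person. Outcome data depend on an event: "Once an acute care visit for an uncomplicated VOC has occurred, the following data will be collected". Section 5 opens eligibility to "All individuals with confirmed SCD who live within 60 miles of the study center or who already receive regular care" at a participating center. The only exclusion tied to infrequent pain applies to patients who are stable on chronic transfusion and have had no painful episode for two years.

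Section 7 (Notation) places each participant in one group, ED or IC, with one observed outcome.

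**The concern.** Being retained and being analysable are different things in this design. A participant can answer every monthly call for 18 months, count as followed up, and never attend an ED or IC with an uncomplicated VOC. That person has no disposition, no time to first dose, no 30-minute reassessment and no visit survey. They also have no treatment group and no pain rating on arrival, which the propensity model needs.

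Eligibility allows such people in. Patients with rare crises are screened out only if they are also on chronic transfusion. Participants whose only acute visits are for complicated VOC or for another reason also supply no eligible visit.

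The documents give no expected no-visit share. They do not say that the 18% includes it, and they do not say that enrolment continues until 410 participants have a visit. What is at stake is the stated analysable number and the power attached to it.

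**Working it through.** **Inputs from section 7a:** admission 50% and 27% (difference 0.23); alpha 0.05; power 0.80; ICC 0.02; 4 clusters per arm; 410 required; 18% loss to follow-up. **Assumptions:** two-sided test (sidedness is not stated); equal arms; q, the share of retained participants with no uncomplicated VOC visit, set at 10, 20 and 30% for illustration.

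**Step 1: reproduce the plan's figure.** 410 / (1 - 0.18) = 500, and back again 500 x 0.82 = 410. The division is right and leaves no remainder for any other cause of a missing outcome.

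**Step 2: add the missing factor.** Analysable number = 500 x 0.82 x (1 - q):

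- q = 0: 410
- q = 10%: 410 x 0.9 = 369
- q = 20%: 410 x 0.8 = 328
- q = 30%: 410 x 0.7 = 287

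**Step 3: power at those numbers.** Section 7a names no formula, so two common ones are shown. With m = N/8 participants per site per arm, the variance of the difference is V = S x [1 + (m - 1) x 0.02] / (4m). S is 0.50 x 0.50 + 0.27 x 0.73 = 0.4471 (unpooled) or 2 x 0.385 x 0.615 = 0.4736 (pooled). Let d = 0.23 / sqrt(V).

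- Cluster t-test: 2 x (4 - 1) = 6 df, noncentral t with noncentrality d.
- Normal design-effect: power = Phi(d - 1.96).

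Example at 410, unpooled: m = 51.25, design effect 2.005, V = 0.4471 x 2.005 / 205 = 0.00437, d = 3.48. The normal form gives Phi(1.52) = 94%; the 6-df t gives 82%.

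| q | Analysable | 6-df cluster t (pooled to unpooled) | Normal design-effect (pooled to unpooled) |
|---|---|---|---|
| 0 | 410 | 80 to 82% | 92 to 94% |
| 10% | 369 | 78 to 80% | 91 to 92% |
| 20% | 328 | 76 to 78% | 89 to 91% |
| 30% | 287 | 73 to 75% | 87 to 89% |

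Under the normal form, power stays near or above 80% until about half of retained participants have no visit (205 analysable: 79 to 81%).

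**Step 4: check the 410 itself.** 41 per site per arm x 4 sites x 2 arms = 328, not 410; 410 would be 41 x 5 x 2. If 328 is the requirement, 328 / 0.82 = 400, and 500 enrolled meets it as long as 410 x (1 - q) is at least 328, that is, q up to 20%.

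The formula behind the plan cannot be recovered with confidence. The pooled 6-df t-test needs 408 and the unpooled one 368. A variant that adds one cluster per arm needs 39 to 44 per site per arm (312 to 352 in total).

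**The case against.** The strongest reply is that 410/0.82 = 500 is correct and that the shortfall may be small. Both parts have force. There is no slip in the division; the defect is an unstated assumption. The size of q cannot be taken from the documents.

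One might point to section 3, where patients at one infusion center averaged 2.5 visits a year, or 3.75 over 18 months. That average covers only people who had at least one visit (range 1 to 84), so it says nothing about the share with none. As illustration only, a mean of 3.75 implies 2% with no visit under a Poisson distribution, but 12 to 46% under a negative binomial with dispersion parameter 2 to 0.3. Repeat visits by frequent users do not fill the gap either, because section 7 allows one outcome per participant and section 7a counts participants.

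A reader might infer that the study falls below 80% power. The documents do not support that. It happens at modest q under the 6-df t-test but not under the normal calculation, and section 7a commits to neither. The planned analysis, a propensity-weighted clustered estimator with bootstrap standard errors, is neither of these tests. Nor do the figures above include precision lost to weighting or unequal arms, so they do not prove that there is slack.

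A reader might also infer that entry should require a VOC visit in the previous year, using the baseline item "Self-reported number of acute care visits and hospitalizations in the prior 12 months". That item counts all acute care visits and hospitalizations, not VOC visits. A past visit does not guarantee a later one, and the rule would change the study population.

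The conflict between 328 and 410 also stands. At q = 20% the study would still have the 41 per site per arm that section 7a asks for. This limits how much weight the shortfall can bear, but it does not make 500 deliver the stated 410.

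**Conclusion.** The point holds in a limited form. As written, 500 enrolled gives 410 analysable participants only if q = 0, which the design does not ensure and the plan does not claim. For each 10 points of q, 41 analysable participants are lost.

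The cost in power over q = 0 to 30% is about 7 points under a 6-df cluster t-test and about 5 under a normal design-effect calculation. Only the first crosses 80%. These figures rest on an assumed q, equal arms, a two-sided test and the stated ICC. Whether the loss matters cannot be settled until the plan decides between 328 and 410.

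**What to change.** In section 7a:

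1. Reconcile 41 per site per arm over 4 sites and 2 arms (328) with the stated 410, and name the formula used.
2. State the expected share of retained participants with no uncomplicated VOC visit in 18 months, with its source, or a range if no source exists.
3. Restate the expected analysable number as 500 x 0.82 x (1 - q), and give power at that number by the named formula.

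The cost is a few sentences and a slightly less favourable stated figure. No added enrolment and no new entry criterion are needed.
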